7.0 Risks

Potential Risks

- Frequent blood draws can lead to anemia.
- 2. Withholding BP medications may result in elevation in BP. We will monitor BP every one to three days after stopping or decreasing these medications. If the BP is too high (see **Protection against risk**) or there are symptoms of high BP, the study will be stopped and prior medications will be restarted.
- 3. Putting a catheter into a vein may cause bleeding, bruising, or infection (uncommon). We will use careful and sterile technique to minimize these side effects.
- 4. Adipose and muscle tissue biopsies may cause bleeding, bruising, pain, or infection (uncommon). Only trained investigators will complete these procedures. We will use sterile technique to minimize the risk of infection, and local anesthesia (lidocaine) will be used to minimize pain. We will monitor subjects for one hour after the biopsies.
- 5. Infusion of glucose may cause hyperglycemia. Symptoms of high blood sugar are hunger, thirst, frequent urination, dry mouth, and dry skin. Blood will be monitored during and for 2 3 hours after clamp completion to ensure blood sugar remains in the normal range. IV glucose may cause irritation of the vein, including redness and pain. We will give the glucose through a bigger vein to decrease this risk.
- 6. Infusion of insulin may cause hypoglycemia. Symptoms of low blood sugar are nausea, extreme hunger, feeling nervous or jittery, cold, clammy, wet skin and/or excessive sweating not caused by exercise, a rapid heartbeat, and numbness or tingling of the fingertips or lips, and trembling. Glucose (dextrose 20%) will be infused during periods of insulin administration, and glucose will be monitored every five min to maintain normal plasma glucose. After study completion, insulin will be stopped, a meal will be given, and intravenous glucose will be tapered. Blood glucose will be monitored for 2-3 hours after the study until it stabilizes within the normal range.
- 7. Eating a controlled diet for one day may be inconvenient.
- 8. GSK2256294 is an investigational drug. To date there are no safety concerns based on Phase I and II trials in humans. There has been skin irritation at the site of ECG lead placement during GSK2256294. There may be risks that we do not know about at this time. There is a theoretical risk that inhibiting sEH and increasing EETs could promote angiogenesis in pre-existing cancer.

Protections against risk

1. A nurse or physician will be present at all times during the study days.

- 2. Medication withdrawal (hypertensive subjects): Anti-hypertensive medications will be discontinued three weeks prior to the study day to avoid confounding effects on sEH activity or EETs. We have excluded individuals with resistant hypertension to minimize risk. Whenever appropriate, medications will be tapered before they are discontinued. During the washout period, BP will be measured every one to three days. If at any time the seated systolic BP is >170 mmHg or the seated diastolic BP >110 mm Hg or if a hypertensive subject develops symptoms of high BP regardless of the pressure, that subject will be discontinued from the study and his or her anti-hypertensive medications will be restarted. In our experience, approximately five percent of enrolled subjects may be excluded by these BP criteria. Excluded subjects will be replaced.
- 3. Subjects with a history of a hematocrit less than 35% will be excluded from study.
- 4. Only trained investigators will complete adipose and muscle tissue biopsies. We will use sterile technique to minimize the risk of infection, and local anesthesia (lidocaine) will be used to minimize pain. We will monitor subjects for one hour after the biopsies.
- We will monitor glucose concentrations frequently during and immediately after hyperinsulinemic-euglycemic clamps. Should hypoglycemia occur, we will administer glucose.
- 6. We have limited the duration of GSK2256294, and we are excluding participants with a history of cancer or precancerous lesions. We are requiring that subjects be current with American Cancer Society Guidelines for the Early Detection of Cancer and also have PSA screening. We are excluding smokers.
- 7. We will monitor subjects actively for new adverse events using a standard questionnaire.

Should any adverse effects of GSK2256294 become known during the study, we will notify the IRB, we will revise the protocol and consent form as appropriate, and we will advise and re-consent study participants

8.0 Reporting of Adverse Events or Unanticipated Problems involving Risk to Participants or Others

All protocols will be reviewed and approved by the Vanderbilt Institutional Review Board (IRB) before any subject is enrolled. The Principal Investigators will closely oversee the protocol in conjunction with the dedicated research nurse and Co-investigators.

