4.0 Inclusion/Exclusion Criteria

Inclusion criteria

- 1. Men and women,
- Age 21 to 60 years, and
- 3. Pre-diabetes as defined by
 - a. Fasting plasma glucose 100-125 mg/dL, or
 - b. Two-hour plasma glucose 140-199 mg/dL, or
 - c. HbA1c 5.7-6.4%
- 4. BMI \geq 30 kg/m², inclusive
- 5. For female subjects, the following conditions must be met:
 - a. Postmenopausal status for at least one year, or
 - b. Status-post surgical sterilization, or
 - c. If of childbearing potential, utilization of adequate birth control and willingness to undergo serum β -hcg testing prior to drug treatment and on every study day.

Exclusion criteria

Subjects presenting with any of the following will not be included in the study:

- Diabetes type 1 or type 2, as defined by a fasting plasma glucose of 126 mg/dL or greater, a two-hour plasma glucose of 200 mg/dL or greater, a HbA1c >6.4%, or the use of anti-diabetic medication
- 2. Subjects who have participated in a weight-reduction program during the last six month or whose weight has increased or decreased more than two kg over the preceding six months
- 3. Resistant hypertension, defined as hypertension requiring the administration of more than three anti-hypertensive agents including a diuretic to achieve control
- 4. Use of spironolactone
- 5. Pregnancy or breast-feeding
- 6. Any significant history of smoking, as defined by smoking one pack-year over any cumulative time or smoking any amount within the last ten years
- Any history of cancer including skin cancer, any history of a precancerous lesion, abnormal PSA, or lack of screening adherent to American Cancer Society Guidelines for the Early Detection of Cancer
- 8. Cardiovascular disease such as myocardial infarction within six months prior to enrollment, presence of angina pectoris, significant arrhythmia, congestive heart failure (left ventricular hypertrophy acceptable), deep-vein thrombosis, pulmonary embolism, second- or third-degree heart block, mitral valve stenosis, aortic stenosis, or hypertrophic cardiomyopathy
- 9. Abnormal corrected QT interval on screening ECG (QTc).
- 10. Treatment with anticoagulants
- 11. History of serious neurologic disease such as cerebral hemorrhage, stroke, or

- transient ischemic attack
- 12. History or presence of immunological or hematological disorders
- 13. Diagnosis of asthma requiring regular inhaler use
- 14. Clinically significant gastrointestinal impairment that could interfere with drug absorption

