- 15. Impaired hepatic function (aspartate amino transaminase [AST] and/or alanine amino transaminase [ALT] >3.0 x upper limit of normal range)
- 16. History of gastrointestinal bleed
- 17. Estimated glomerular filtration rate (eGFR)<60 mL/min/1.73 m² or with an albumin-to-creatinine ratio (UACR) ≥300µg/mg, where eGFR is determined by the four-variable Modification of Diet in Renal Disease (MDRD) equation, where serum creatinine is expressed in mg/dL and age in years: eGFR (mL/min/1.73m²)=186 Scr^{-1.154} age^{-0.203} (1.212 if black) (0.742 if female)
- 18. Hematocrit <35%
- 19. Any underlying or acute disease requiring regular medication which could possibly pose a threat to the subject or make implementation of the protocol or interpretation of the study results difficult
- 20. Treatment with chronic systemic glucocorticoid therapy
- 21. Treatment with lithium salts
- 22. History of alcohol or drug abuse
- 23. Treatment with any investigational drug in the month preceding the study
- 24. Mental conditions rendering a subject unable to understand the nature, scope, and possible consequences of the study
- 25. Inability to comply with the protocol, e.g., uncooperative attitude, inability to return for follow-up visits, and unlikelihood of completing the study

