6.0 Study Procedures

Rationale: Our preliminary studies indicate that the *EPHX2* loss-of-function variant (Arg287GIn) is associated with a 22% decrease in plasma sEH activity and enhanced insulin sensitivity. Studies in animal models suggest that sEH activity is increased in insulin-sensitive tissues in obesity, whereas epoxygenase activity is decreased. A potent pharmacological inhibitor of sEH has the potential to decrease sEH activity in insulinsensitive tissue even in obese subjects. In this Aim we will determine whether pharmacological sEH inhibition reduces sEH activity in insulin-sensitive tissues and whether pharmacological sEH inhibition enhances insulin sensitivity through increased insulin signaling or increased blood flow.

Subjects:

We will study 34 obese (BMI \geq 30 kg/m²) and pre-diabetic subjects, age 21 through 50 years. We will study fifty percent black subjects, fifty percent white subjects, and fifty percent women. Subjects with any history of cancer including skin cancer, cardiovascular disease (other than hypertension), renal, pulmonary, endocrine (other than insulin resistance or hyperlipidemia), or hematologic disease will be excluded. Individuals with diabetes, resistant hypertension, or any history of smoking will be excluded. Pregnancy will be excluded. Detailed inclusion and exclusion criteria appear in **Human Subjects.**

Protocol:

Once informed consent has been obtained, subjects will report to the CRC after an overnight fast, and we will obtain a medical history and complete a physical examination. We will obtain screening laboratory and an ECG. Between screening and the first study day, subjects will return to the CRC in the fasting state to undergo measurement of waist and hip circumference, a 75-gram OGTT, and body composition measurement by Dual Energy X-ray Absorptiometry (DEXA, see Standard Techniques). Because this is a crossover study, hypertensive participants of this Aim will continue to take their anti-hypertensive medications, and the doses will be maintained constant throughout the study.

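### Section 6 keeps hypertensive participants on constant-dose anti-hypertensives, Section 7 stops the same drugs three weeks before the study day, and nothing says which rule governs

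*Protocol*

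**What the plan says.** Section 6.0 (Protocol) sets the rule for the crossover and gives its reason: "Because this is a crossover study, hypertensive participants of this Aim will continue to take their anti-hypertensive medications". The same sentence holds doses constant for the whole study.

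Section 7.0 says otherwise in two places. Potential Risks, item 2, lists a rise in blood pressure from withheld drugs as a risk to participants. Protections against risk, item 2, headed as medication withdrawal in hypertensive subjects, states: "Anti-hypertensive medications will be discontinued three weeks prior to the study day to avoid confounding effects on sEH activity or EETs". It then gives a working procedure:

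- taper where appropriate;
- measure blood pressure at intervals of one to three days;
- take the subject out of the study and restart the drugs if seated systolic pressure exceeds 170 mmHg, seated diastolic pressure exceeds 110 mmHg, or a hypertensive subject has symptoms of high pressure;
- replace those excluded.

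It adds that, from experience, about five percent of those enrolled may be lost to these criteria.

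Treated hypertensive people can enrol. Section 6.0 (Subjects) carves hypertension out of the cardiovascular exclusion: "Subjects with any history of cancer including skin cancer, cardiovascular disease (other than hypertension), renal, pulmonary". Section 4.0 removes only resistant cases ("hypertension requiring the administration of more than three anti-hypertensive agents including a diuretic to achieve control"), users of one drug ("Use of spironolactone"), and anyone caught by the broader exclusion 19 ("Any underlying or acute disease requiring regular medication which could possibly pose a threat to the subject").

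**The concern.** One participant cannot both stay on a constant dose and be taken off the drug. A site reading the procedures section and a site nurse reading the risk section would treat the same person differently, and each would be following the protocol.

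The main stake is participant safety. If Section 6 is the intended rule, every withdrawal carried out under Section 7 exposes someone to a risk that the protocol itself lists, with no purpose in this trial.

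The second stake is consistency of conduct. Section 7 justifies withdrawal by possible confounding of sEH activity and EETs, which the SAP lists among the secondary endpoints. Those comparisons could be disturbed if a subject were on anti-hypertensives at one study day and off them at the other.

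**Working it through.** **1. Do the two texts cover the same people and drugs?** Yes. Both refer to hypertensive participants and to anti-hypertensive medication. Section 7 makes no exception for this study, and the protocol describes no other aim to which its rule could belong.

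**2. Does any text reconcile them?** No. Section 6 lays out the sequence of visits without a withdrawal step. Section 7 does not mention the constant-dose rule. The DSMC text in Section 8.0 has the committee review the protocol beforehand and assess hypertension and hypotension, but it does not say which rule applies. The SAP is silent.

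**3. Which is more plausible?** Section 6. It refers to the present Aim and gives a reason specific to the design: each subject is compared with himself or herself, so background drugs held constant are matched between treatments.

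**4. How long would a participant be off treatment?**

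Inputs:
- withdrawal lead time: 3 weeks (Section 7.0);
- washout from study drug: 7 weeks (Section 6.0);
- treatment period: 1 week, with the study day on day 7 (Section 6.0).

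Interval between study days = 7 + 1 = 8 weeks. This reproduces the eight-week interval in the SAP's Data Analysis Plan.

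| Rule applied | Calculation | Weeks off drug by second study day |
|---|---|---|
| Section 6 | none | 0 |
| Section 7, before one study day only | 3 | 3 |
| Section 7, before both, drugs resumed in between | 3 + 3 | 6 |
| Section 7, before both, drugs not resumed | 3 + 8 | 11 |

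With resumption, the subject would be back on treatment for 8 − 3 = 5 weeks between the two withdrawals. Taper time is not given and would be extra. Only the three-week figure is in the protocol. The 6 and 11 are readings of its silence on restarting.

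**5. Effect on the paired comparison.** The SAP compares drug with placebo within subject, by paired t-test or signed-rank test. If a subject's anti-hypertensive status is the same at both study days, on or off, the rule contributes no systematic difference between treatments. A problem arises only if status differs between a subject's two days.

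**The case against.** The best defence is that the conflict is unlikely to do harm. Section 6 is the specific rule, and staff working through its visit sequence would meet no instruction to stop drugs. Section 7 may be text carried over from related work. IRB approval and DSMC protocol review come before any study procedure. Even under Section 7 the withdrawal is tapered, monitored and bounded by stopping limits.

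Much of this stands, and it lowers the probability of harm. It does not remove the conflict. Section 7 is a complete procedure that a nurse could carry out as written, and neither oversight step says which rule holds. If the text is left over, it should come out. If it is intended, Section 6 lacks a step. One section must change either way.

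Three stronger readings are tempting but not supported:

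- **That Section 7's singular study day shows it was written for a one-visit design.** Section 6 uses the same singular for each period, for the overnight urine collection and for the start of the washout. The wording is not evidence of origin. It also means that a three-week total is not the obvious literal reading. Three weeks before each study day is at least as natural.
- **That the protocol prescribes 6 or 11 weeks off treatment.** It does not. Those totals depend on a restart rule that is not stated.
- **That about two of the 34 planned subjects would be lost.** Section 6 gives the size ("We will study 34 obese"), and 0.05 × 34 = 1.7. But the rate is from past experience, is worded as a possibility, and applies to those enrolled. Those excluded are replaced, so 34 need not be the denominator, and the hypertensive share here is unknown. Nor does it measure harm, since these subjects reach a protective limit and restart treatment.

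**Conclusion.** The protocol is internally inconsistent on a matter of participant safety and is wrong as written. The documented size is zero weeks off prescribed anti-hypertensives under Section 6 against three weeks before a study day under Section 7. If withdrawal applied before both study days, the total would depend on the missing restart rule, for example 6 weeks with resumption or 11 without. The number of participants affected cannot be given, because the documents do not state how many will be hypertensive.

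That Section 6 is the intended rule is a judgement from its wording, not something the protocol declares.

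A reader might infer that the primary insulin sensitivity result is biased or that power is reduced. The documents do not show either. The paired contrast stays balanced if either rule is applied alike before both study days. The secondary sEH and EET comparisons are at risk only if a subject's drug status changes between the two days.

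**What to change.** Keep the Section 6 rule and amend Section 7.0:

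1. Delete the withholding risk in Potential Risks, item 2.
2. In Protections against risk, item 2, delete the discontinuation, taper and five-percent text.
3. Retain the limits of >170 mmHg systolic and >110 mmHg diastolic, and the rule on symptomatic hypertension, as a general participant stopping rule. Reword it so that it no longer speaks of restarting withdrawn drugs. These are the only numeric blood pressure stopping limits in the documents, and hypertensive participants will still enrol, so they should not be lost with the rest of the item.
4. Record anti-hypertensive drugs and doses at both study days.

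Replacement of non-completers (Section 5.0) and DSMC review of hypertension and hypotension (Section 8.0) are unaffected.

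If withdrawal is in fact intended, delete the constant-dose sentence from Section 6.0 instead and add the withdrawal step there. State that it applies identically before both study days and whether the drugs are restarted in between.

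The cost of the preferred fix is amendment wording and one record field per study day, with no extra participants or visits.

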The DSMC will also receive quarterly reports of enrollment, protocol adherence, data quality, and adverse events via e-mail. The DSMC will review all serious adverse events. Any serious adverse event will be reported to the DSMC, IRB, NIH, and FDA within 7 days of the PI's notification of the event. Any untoward medical event will be classified as an adverse event, regardless of its causal relationship with the study. An adverse event will be classified as serious if it a) results in death, b) is life-threatening, c) requires inpatient hospitalization or prolongation of existing hospitalization, d) results in persistent or significant disability or incapacity, or e) is a congenital anomaly or birth defect. The DSMC may choose to become unblinded; however, it is expected that such unblinding would not occur without reasonable concern related either to patient safety or to data validity.

Non-serious, unexpected adverse events will be reported to the IRB at the time of annual continuing review. If required, appropriate changes will be made to the consent form. Adverse events will be graded as mild (no limitation of usual activities), moderate (some limitation), or severe (inability to carry out usual activities) and attributed according to the relationship to the study drug and/or procedures as Not related, Unlikely, Possible, Probable, or Definite. Any protocol deviation will be reported at the time of annual continuing review. Summary reports will be submitted to the IRB at least annually and will contain a) the number of adverse events and an explanation of how each event was handled, b) the number of complaints and how each complaint was handled, c) the number of subject withdrawals and an explanation

of why the subject withdrew or was withdrawn, and d) the number of protocol violations and how each was handled.
now each was handled.

9.0 Study Withdrawal/Discontinuation

If at any time during the study, a subject develops any symptoms related to study participation that subject will be withdrawn from the study. If, in the opinion of the investigator, a subject is non-compliant, that subject will be withdrawn from the study. Subjects who are withdrawn will be followed until symptoms have resolved.

10.0 Privacy/Confidentiality Issues

A unique identification case number will be used to protect the confidentiality of the study participants. Only case numbers will be included in spreadsheets used for the statistical analysis.

We will use the web-based Vanderbilt Research Electronic Data Capture (REDCap) system to design electronic data collection forms. These forms will be pilot tested before use. Data will be input into a protected, web-based case report form (which can be readily downloaded into SAS, STATA, R, or SPSS). The form allows for direct data entry by investigators and is designed to minimize errors and erroneous values. Results from the Vanderbilt clinical laboratory can also be directly imported to REDCap, which further reduces typographical data entry errors. Expected ranges are pre-specified to prevent errors such as the shifting of decimal points. The program includes a computerized audit trail so that the identity of individuals entering or changing data and, in the case of changes, both original and revised data are saved. Data are backed up daily. Clinical data, including clinical laboratory, will be entered by the research nurse. Research laboratory data will be entered by a predoctoral student in the laboratory.

11.0 Follow-up and Record Retention

All records will be retained for 7 years following publication of the data. After that time, records may be archived for an additional 5 years and then shredded.

Soluble Epoxide Hydrolase Inhibition and Insulin Resistance NCT03486223

Statistical Analysis plan from IRB approved version dated Date 8/11/2021

Statistical Analysis Plan:

The primary analysis will focus on the effect of GSK2256294 versus placebo on insulin sensitivity. Secondary endpoints will include the effect of GSK2256294 on insulin-stimulated FBF and renal blood flow; insulin-stimulated AKT phosphorylation in muscle and adipose tissue; tissue CD31 and VEGF expression; insulin-stimulated suppression of hepatic glucose production; plasma, muscle, adipose tissue sEH activity and EETs; and tissue and circulating adipokines and cytokines.

Sample Size and Power Calculation: In our prior study of the relationship between EPHX2 Arg287GIn genotype and insulin sensitivity in obese individuals the insulin sensitivity index was 8.24±4.6 mg/kg/min per μ U/mL*100 (mean±SD) in carriers of the 287GIn allele versus 3.54±1.3 mg/kg/min per μ U/mL*100 in Arg/Arg homozygotes. Conservatively assuming a correlation of 0.5 between two measures of insulin sensitivity in the same subject, the study can detect a within-subject difference of 3.76 (80% of the above difference) or larger (with an SD for the within-subject difference of 4.6) with 80% power and 0.05 type 1 error rate with 34 subjects. The sample size was chosen to allow us to detect effects of treatment within racial or gender group. We need 16 per group to have 86% power to detect difference in insulin sensitivity noted above. Moreover, with 34 subjects, we have 80% power to detect a change in insulin-stimulated FBF of 0.9 mL/min/100 mL in the cross-over study, assuming a within-subject correlation coefficient of 0.5. We will have 80% power to see an increase in insulin signaling (ratio of pAKT to AKT) of 0.07 (0.91±0.13 versus 0.84±0.13 in Arg/Arg).

Data Analysis Plan: For the within-subject comparison of GSK2256294 versus placebo, we will use either a paired t-test or Wilcoxon-signed rank test. We do not expect a carry-over effect with the eight-week period between study days. Nevertheless, we will test for a carryover effect using the T-test approach proposed by Jones and Kenward. Should a carry over effect exist, we will either use period one data to estimate the treatment effect, or estimate the treatment effect using data from both periods with the understanding that the potential carry over effect may negatively bias the estimate of the treatment difference. Our conservatively planned sample size will help preserve study power. Although we also do not anticipate a period effect, we will use the T-test approach of Hills and Armitage to test for one.

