5.0 Enrollment/Randomization

Assignment to treatment order will be randomized and blinded to the investigators and subjects. Subjects will be randomly assigned to drug order using a permuted-block randomization algorithm. [name], study biostatistician, will provide an allocation schedule. Vanderbilt Investigational Drug Services (IDS) will be responsible for the storage, preparation, and labeling of all investigational agents and for maintaining accurate drug storage and dispensing logs. The Clinical Research Pharmacist will devise standard operating procedures for the pharmacy to follow with regard to preparing, labeling, blinding, and dispensing study drug.

After subjects have been consented and screened, the investigator or research nurse will fax a copy of the consent form and a prescription containing check boxes for the inclusion and exclusion criteria to Vanderbilt IDS. The pharmacist will confirm that consent was obtained and the subject met entry criteria, assign the subject a randomization number, and provide the investigator with labeled study drug as indicated in the protocol. An extra label containing the randomization number will be attached to each study drug. The investigator will affix this extra label to the subject's records. The Investigational Pharmacy will retain a secure set of sealed envelopes containing the treatment assignment. These will be opened in the event of a clinical scenario which necessitates unblinding, as determined by the PI and the DSMC (see Data and Safety Monitoring Plan). Subjects randomized who do not complete the whole protocol for any reason will be replaced.

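### The 80% power stated for 34 subjects on the primary endpoint does not follow from the SAP's own inputs, which give 99.6%

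*SAP*

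**What the plan says.** The SAP paragraph on sample size and power starts from an earlier genotype study in obese individuals. The insulin sensitivity index there was 8.24 (SD 4.6) in carriers of the variant and 3.54 (SD 1.3) in non-carriers, in mg/kg/min per µU/mL × 100. The SAP takes 80% of that gap, 3.76, as the treatment difference. It assumes a correlation of 0.5 between a subject's two measurements and concludes that this difference is detectable "with an SD for the within-subject difference of 4.6) with 80% power and 0.05 type 1 error rate with 34 subjects". It does not say whether the test is one- or two-sided.

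The paragraph then gives the reason for the number: "The sample size was chosen to allow us to detect effects of treatment within racial or gender group". It adds: "We need 16 per group to have 86% power to detect difference in insulin sensitivity noted above".

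For the treatment comparison, the SAP's Data Analysis Plan says "we will use either a paired t-test or Wilcoxon-signed rank test". It has a fallback if carryover is found: "Should a carry over effect exist, we will either use period one data to estimate the treatment effect". On dropout, Protocol section 5.0 says: "Subjects randomized who do not complete the whole protocol for any reason will be replaced".

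**The concern.** Two power figures stand a sentence or two apart and run in the wrong order: 86% with 16 subjects and 80% with 34, apparently for the same difference. Power cannot fall as the sample grows, so at least one figure is wrong or rests on an unstated basis.

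This is the only full-sample power statement for the primary endpoint. A reader will take 3.76 as the smallest effect the trial was sized to find with 80% power, and will judge a null result by it. The Data Analysis Plan also relies on the sample size being conservative if carryover appears, so the actual margin should be on record.

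**Working it through.** **Inputs.** All are from the SAP's sample size paragraph unless noted.

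- Difference: 0.8 × (8.24 − 3.54) = 0.8 × 4.70 = 3.76, as stated.
- SD of the within-subject difference: √(2 × 4.6² × (1 − 0.5)) = 4.6, as stated. The correlation of 0.5 is therefore already inside the 4.6.
- Type 1 error 0.05; two-sided assumed, one-sided also computed.
- 34 subjects, each receiving both treatments (Protocol 6.0).
- Test: paired t, or Wilcoxon signed-rank (SAP Data Analysis Plan).

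**Formula.** Paired t-test power comes from the noncentral t distribution with n − 1 degrees of freedom and noncentrality (3.76/4.6) × √n.

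**Step 1: the plan's 86%.** At n = 16 the noncentrality is 0.817 × 4 = 3.27 and two-sided power is 86.3%. The SAP's figure reproduces. On this paired basis the difference referred to must be 3.76, because 4.70 would give 96.8%.

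**Step 2: the plan's 80%.** At n = 34 the noncentrality is 0.817 × 5.83 = 4.77 and two-sided power is 99.6%. Simulation of the paired t-test gives 99.6% as well. The SAP's figure does not reproduce.

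| Subjects | Two-sided paired t power for 3.76, SD 4.6 |
|---|---|
| 13 | 77.2% |
| 14 | 80.7% |
| 16 | 86.3% |
| 17 | 88.5% |
| 34 | 99.6% |

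**Step 3: what 80% does correspond to.** Solving for the difference at n = 34 gives 2.28 two-sided (2.00 one-sided). Then 2.28/4.70 = 48% of the genotype gap, against the 80% stated, and 3.76/2.277 = 1.65.

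**Step 4: can another reading give 80% at 34 subjects?**

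| Variant | Power for 3.76 |
|---|---|
| One-sided | 99.9% |
| Wilcoxon, effective n = 34 × 3/π | 99.5% (simulations 99.4% to 99.6%) |
| Crossover test with 32 degrees of freedom | 99.6% |
| Type 1 error 0.01 | 97.4% |
| Correlation 0.25 (SD of difference 5.63) | 96.5% |
| Correlation 0 (SD of difference 6.51) | 90.5% |
| Unpaired 17 vs 17, SD 4.6 | 63.7% |
| Unpaired 17 vs 17, SD 3.38 | 88.2% |

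The SD of 3.38 is √((4.6² + 1.3²)/2). For 80% in the paired test, the SD of the difference would have to be about 7.6, a value found nowhere in the documents. With a per-measurement SD of 4.6 that needs a negative correlation: 1 − 7.6²/(2 × 4.6²) = −0.36. Dropout does not explain the gap either, since non-completers are replaced.

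An unpaired comparison of 16 vs 16 for the full 4.70 with SD 4.6 does give 79.9%, but it uses a different difference, design and sample size from those stated.

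**Step 5: does the conflict depend on how the 86% was obtained?** The SAP does not give its basis. An unpaired 16 vs 16 comparison with SD 3.38 also gives 86.1%. On that basis 34 subjects (17 vs 17) would give 88.2%. Neither basis yields 80% at 34.

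**The case against.** The strongest defence is that 80% is a floor. If the sentence means at least 80% power, it is loose but not false. The pAKT/AKT statement in the same paragraph gives this some support: if its SD of 0.13 is also the SD of the difference (an assumption), a change of 0.07 at n = 34 has 86% power, and the SAP again writes 80%. The figure may be a nominal target. But the sentence pairs a minimum difference with a power, and the allowance for larger values attaches to the difference, not to the power. Read that way, the minimum is 2.28. A true value of 99.6% is also a long way above a floor of 80%.

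A second defence is that nothing depends on the figure. The error is in the safe direction, and the number 34 has its own justification in the subgroups. Protocol 6.0 plans half black and half white subjects and half women, so about 17 per subgroup, where paired power for 3.76 is 88.5%. This stands, and it is why the remedy is confined to wording.

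A third point is that writing more than 99% into the SAP could overstate certainty. The SD comes from a between-subject figure and an assumed correlation, and the effect is borrowed from a genotype contrast. At 3.76 it exceeds the non-carrier mean of 3.54. This stands too: the corrected figure must carry its assumptions, and the 80% detectable difference should appear beside it.

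**Conclusion.** The concern holds. On the SAP's own inputs, 34 subjects give 99.6% power for 3.76, not 80%; at 80% power they detect 2.28. The conclusion does not depend on sidedness or on the choice between the two named tests. The exact values assume a two-sided 0.05 paired t-test and an SD of the difference of 4.6.

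The error understates power on those inputs. This check does not validate the inputs themselves.

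The corrected figure covers only the analysis that uses both periods. The period-one fallback is a between-subject comparison, and the SAP states no SD for it. With 17 vs 17 (equal allocation assumed), its power for 3.76 would be 64% with an SD of 4.6 or 88% with an SD of 3.38.

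This should be corrected, but it is no threat to the design.

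**What to change.** Replace the power sentence with text along these lines:

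> Assuming an SD of 4.6 for the within-subject difference and a two-sided 0.05 paired t-test on both periods, 34 subjects give more than 99% power for a difference of 3.76 and 80% power for 2.28. The number was set so that treatment effects can be examined inside each race and sex subgroup, where 16 subjects give 86% power for a within-subject difference of 3.76. These figures do not apply to the analysis of period one alone.

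Before adopting it, the sponsor should confirm two things the SAP leaves open: that the test is two-sided, and that the 86% is the paired calculation within a subgroup.

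The cost is SAP wording only. Keep 34 subjects, the endpoint and the test as they are.
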